6.2. Analysis of the Primary Endpoint

The number and percentage of subjects with 12-month TLF will be presented. A one-sided upper 95% confidence interval of the Resolute Onyx 2.0 mm stent 12-month TLF rate will be calculated through binomial (exact) method. If this upper limit is below 19%, the clinical objective will be considered to have been met.

With regard to clinical outcomes analysis, in subjects receiving treatment of two lesions with a Resolute Onyx 2.0 mm stent, the lesion to be included in the primary analysis, the “analysis lesion”, will be randomly selected at the time of analysis. For subjects receiving treatment of a Resolute Onyx 2.0 mm stent and another size stent, the primary analysis will include the lesion treated with the 2.0 mm stent, regardless of the other stent size. A secondary analysis will be conducted for all target lesions.

The algorithm to randomly select the “analysis lesion” is specified below:

The seed of the ranuni function will be specified in the statistical analysis plan prior to the database lock and will not be changed. Therefore, bias cannot be introduced in the random selection of the lesion in the primary analysis.

A random lesion will be chosen for the primary analysis as follows:

1. Sort the lesions according to patient number and CASS site (with one observation per patient/CASS).
2. Assign a random number to each observation using the SAS ranuni function (the seed will be pre-specified in the statistical analysis plan).
3. Resort the lesions according to patient number and newly created random number.
4. Choose the first patient/CASS observation according to the sort in step 3.

As a supplementary analysis, to account for missing data, subjects who drop out prior to 330 days post-procedure and do not experience TLF will have their 12-month TLF-free status (yes/no) imputed using the multiple imputation, tipping point analysis and worst case analysis.

The multiple imputation approach will use SAS V9 PROC MI. The covariates to be used in the imputation model are lesion-length, baseline RVD, age, sex, diabetes, history of MI, Canadian Cardiovascular Society Angina Class, and TLF status at visits prior to dropout. One hundred imputed data sets will be generated. An overall TLF rate and its one-sided upper 95% confidence intervals will be generated across the one hundred imputed data sets. For the subjects have 2 or more target lesions, the longest lesion length and the smallest baseline RVD will be used in the imputation model.

The tipping point analysis will impute the most 12-month TLF-missing status as yes so that the one-side upper 95% confidence interval of 12-month TLF rate will be less than or equal to the performance goal of 19%.

The worst case analysis will impute all the 12-month TLF-missing status as yes then calculate the one-side upper 95% confidence interval of 12-month TLF rate to compare the performance goal of 19%.

Statistical non-significance in the primary endpoint for gender comparisons will confirm the homogeneity by gender in this trial (see analysis of homogeneity below).

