5.4.6 Treatment Failure

Following subject enrollment, study stent(s) that enter the guide catheter and fail to be implanted at the intended location are considered treatment failures and will be recorded in the eCRF. In the event of a failure to implant at least one study stent, the Investigator may choose to treat the target lesion(s) with any approved stent. Treatment failures will be followed-up for safety purposes through 12-months and will be included in the intent-to-treat (ITT) population. The subject will undergo the follow-up assessments listed in [Section 5.6](#) through the 12 month follow-up assessment.

Note: Damaged or failed Resolute Onyx Stent Systems (including ancillary devices) must be returned to the Medtronic Product Experience Management Department per instructions provided by Medtronic.

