7.4 Analysis of the Primary Endpoint

The number and percentage of subjects with 12-month TLF will be provided. A one-sided upper 95% confidence interval of the Resolute Onyx 2.0 mm stent 12-month TLF rate will be calculated through binomial (exact) method. If this upper limit is below 19%, the clinical objective will be considered to have been met.

With regard to clinical outcomes analysis, in subjects receiving treatment of two lesions with a Resolute Onyx 2.0 mm stent, the lesion to be included in the primary analysis, the “analysis lesion”, will be randomly selected at the time of analysis. For subjects receiving treatment of a Resolute Onyx 2.0 mm stent and another size stent, the primary analysis will include the lesion treated with the 2.0 mm stent, regardless of the other stent size. A secondary analysis will be conducted for all target lesions.

Statistical non-significance in the primary endpoint for gender comparisons will confirm the homogeneity by gender in this trial.

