A study deviation is defined as an event where the Investigator or site personnel did not conduct the trial according to the investigational plan, applicable laws or regulations, or the Investigator Agreement.

STUDY STENT

A study stent is defined as the Resolute Onyx 2.0 mm stent.

TARGET LESION

Any lesion treated or attempted to be treated during the study procedure. The target lesion is the treated segment starting 5 mm proximal to the stent and ending 5 mm distal to the stent.

TARGET LESION FAILURE (TLF)

Defined as cardiac death, target vessel myocardial infarction (Q wave and non-Q wave), or clinically-driven target lesion revascularization (TLR) by percutaneous or surgical methods

TARGET LESION REVASCULARIZATION (TLR)

Repeat PCI or CABG to the target lesion. See also clinically-driven target lesion revascularization.

TARGET VESSEL

The arterial segment and any branches and/or parent vessel that possess the target lesion. For this study, the target vessel can only be the left main (protected), LAD, Cx, RCA. Side branches less than 2.0 mm in diameter will not be considered 'significant' and therefore the disease in these vessels will not be considered significant.

RESOLUTE Onyx 2.0 mm Clinical Study**CONFIDENTIAL - May not be reproduced without written permission from Medtronic**

TARGET VESSEL FAILURE (TVF)

The composite endpoint comprised of cardiac death, target vessel myocardial infarction, or clinically-driven target vessel revascularization by percutaneous or surgical methods.

Target vessel failure will be reported when ANY of the following events occur:

- Recurrent MI occurs in territory not clearly attributed to a vessel other than the target vessel.
- Cardiac death not clearly due to a non-target vessel endpoint.
- Target vessel revascularization is determined.

TARGET VESSEL MYOCARDIAL INFARCTION (TVMI)

Target-vessel MI is defined as a MI that occurs in a territory that cannot be clearly attributed to a vessel other than the target vessel.

TARGET VESSEL REVASCULARIZATION (TVR)

Repeat PCI or CABG of the target vessel. See also clinically-driven target vessel revascularization.

THROMBOLYSIS IN MYOCARDIAL INFARCTION (TIMI) CLASSIFICATION¹⁵

TIMI 0	No perfusion.
TIMI 1	Penetration with minimal perfusion. Contrast fails to opacify the entire bed distal to the stenosis for the duration of the cine run.

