3.1. Treatment(s) and Subject Enrollment

At least 100 subjects with ischemic heart disease due to *de novo* stenotic lesions within native coronary arteries that meet the eligibility criteria and sign the informed consent form will be asked to participate in this trial. All subjects who consent will be asked to participate in the 13 month angiographic subset until at least 20 subjects have been enrolled in this subset. Subjects may receive treatment in up to two lesions, if the lesions are located in separate target vessels. Only one lesion may be treated in a single target vessel. Core size lesions should be treated with the currently approved Resolute Integrity stent. All treatment with the study stents is to be performed during a single index procedure.

In the event of one lesion to be treated with a 2.0 mm study stent and another lesion to be treated with a core size (2.25 mm - 4.0 mm) Resolute Integrity stent, the subject should be treated first with the core-sized stent. If the treatment of the first lesion fails or if the subject becomes unstable before a 2.0 mm study stent is attempted (stent introduced into guide catheter), the subject will not be enrolled, will not be followed, and will not be included in the primary analysis of this trial. Another subject should be enrolled to replace this subject for the primary analysis. If the treatment with the 2.0 mm study stent is attempted (stent introduced into guide catheter) but not implanted, the subject will be considered part of the Intention-to-Treat population (ITT) and will be followed through the 12 month endpoint and will be included in the primary analysis of this trial.

For subjects who have more than one lesion planned for treatment, FFR should be performed in the vessel expected to receive the 2.0 mm study stent to demonstrate the functional need for treating such a lesion, unless demonstrated by other means (clinical evidence and/or positive functional study).

The trial will be conducted at a maximum of 25 investigational sites within the United States (US) and Japan. Sites are allowed to enroll a maximum of 20 subjects per site or until study enrollment has been completed, whichever comes first. The expected time of participation in the trial for each subject is three years.

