3.4. Analysis Strategy

Descriptive statistics will be presented for this study. Hypothesis testing with performance goal will be evaluated for primary endpoint.

4. Analysis Populations

Intent-to-Treat (ITT): For this trial, all subjects who sign the written informed consent and also have the study stent (Resolute Onyx 2.0 mm stent) introduced into the guide catheter will be counted in the ITT set, which will be the primary analysis set.

Per-Protocol (PP): The ITT population excluding subjects who do not meet certain key entry criteria (for exclusion criteria below, if any answer is “yes”, the subjects are excluded from PP population):

1. Did not receive any study device
2. Received study device, and another type of DES
3. Did not meet the following inclusion criteria:
 - a. General Inclusion 3: Subject has clinical evidence of ischemic heart disease, For single vessel disease: stable or unstable angina alone is sufficient. For multi-vessel treatment: a positive functional study or FFR to demonstrate functional need in 2.0 mm small vessel.
 - b. Angiographic Inclusion 1: The subject requires treatment of either:
 - i. A single target lesion amenable to treatment with a 2.0 mm stent
 - OR
 - ii. Two target lesions located in separate target vessels, with at least one of the target lesions amenable to treatment with a 2.0 mm study stent

- c. Angiographic inclusion 2: Target lesion(s) must be de novo lesion(s) in native coronary artery(ies)
4. Did not meet the following exclusion criteria:
- a. General exclusion 5: Evidence of an acute MI within 72 hours of the trial procedure:
 - a) Q wave myocardial infarction (QWMI)
 - OR
 - b) Elevated cardiac biomarker values [preferably cardiac troponin (cTn)] with at least one value above the upper reference limit (URL) and with at least one of the following:
 - Symptoms of ischemia
 - New or presumed new significant ST-segment–T wave (ST–T) changes or new left bundle branch block (LBBB)
 - Development of pathological Q waves in the ECG
 - Imaging evidence of new loss of viable myocardium or new regional wall

Note: Subjects with evidence or suspicion of an acute MI (per Investigator or Sub-Investigator determination) must have cardiac enzyme results reviewed prior to enrollment.
 - b. General exclusion 7: Planned PCI of any vessel within 30 days post-index procedure and/or planned PCI of the target vessel(s) within 12 months post-procedure. (no staged procedures)

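### The analysis lesion is chosen by the stent received while the ITT set works by the stent attempted, so a lesion where the 2.0 mm stent failed can be left out of, or unassigned in, the primary TLF count

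*SAP*

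**What the plan says.** Who counts is settled by attempt:

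- **ITT set (SAP 4):** consented subjects who "have the study stent (Resolute Onyx 2.0 mm stent) introduced into the guide catheter will be counted in the ITT set".
- **Failed attempts (SAP 3.1; Protocol 4.0):** when the stent is "attempted (stent introduced into guide catheter) but not implanted, the subject will be considered part of the Intention-to-Treat population (ITT"), is followed to 12 months and is included in the primary analysis.
- **Target lesion (Protocol Appendix 2):** "Any lesion treated or attempted to be treated during the study procedure".

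Which lesion counts is settled by treatment received. SAP 6.2 and Protocol 7.4 give two sentences:

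- **Two 2.0 mm lesions:** "in subjects receiving treatment of two lesions with a Resolute Onyx 2.0 mm stent, the lesion to be included in the primary analysis" is drawn at random.
- **One 2.0 mm stent and one stent of another size:** the SAP sentence begins "For subjects receiving treatment of a Resolute Onyx 2.0 mm stent and another size stent, the primary analysis will include the lesion treated". Its main clause, the same in the Protocol, reads in full: "the primary analysis will include the lesion treated with the 2.0 mm stent, regardless of the other stent size".

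Neither sentence mentions a lesion where the 2.0 mm stent was tried and not placed. Protocol 5.4.6 foresees such failures and has them recorded in the eCRF. On failure to implant at least one study stent, it says that "the Investigator may choose to treat the target lesion(s) with any approved stent". An analysis of all target lesions is planned, but only as a secondary analysis.

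**The concern.** Whether a stent can be placed is known only after enrolment. A rule that selects the lesion by what was finally placed therefore lets a device outcome decide which lesion is scored. Two patterns are affected.

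**Pattern A: Onyx attempted at two lesions, one ends with another size.** The subject now has a 2.0 mm stent and another size, so the second sentence applies and the successful lesion is always selected. The random draw does not apply.

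**Pattern B: core-size lesion treated first, as both documents direct, and the Onyx then fails at the other lesion.** No lesion was treated with the 2.0 mm stent, so neither sentence names an analysis lesion. The subject must nevertheless be in the primary analysis.

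In a subject with a single lesion, the same device failure leaves that lesion in the count. So the handling of a failure depends on whether a second lesion was treated.

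At stake is the count compared with the 19% goal. The trial is open label and the lesion is selected at the time of analysis, so a case left undefined could be settled with outcomes known. The SAP fixes the random seed in advance to exclude that kind of choice.

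**Working it through.** **1. The rule applied case by case**

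| Onyx 2.0 mm attempted at | Outcome | Analysis lesion, read literally | By attempt |
|---|---|---|---|
| One lesion, no second lesion | Fails | That lesion (the only one) | Same |
| Two lesions | Both placed | Random draw | Same |
| Two lesions | One placed, one ends with another size | Placed lesion, always | Random draw from both |
| Two lesions | One placed, the other gets a non-study 2.0 mm stent or none | Not named | Random draw from both |
| One lesion, other has core size | Onyx fails | Not named | The Onyx lesion |

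In the third row the failed lesion's chance of being scored is 0%, against 50% under a draw by attempt. Protocol 2.1 says that 2.0 mm bare metal stents are approved, so the fourth row can occur.

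**2. What can be lost**

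TLF has three components. Cardiac death belongs to the subject and counts whichever lesion is selected. TLR belongs to the lesion and is lost if it occurs at the unselected lesion. TVMI belongs to the vessel. The two lesions lie in separate vessels, so an MI in the unselected vessel may be lost; the SAP does not say.

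**3. The plan's own figure**

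Inputs (SAP 3.3): 100 subjects, 10% loss, so n = 90; goal 19%; assumed rate 9.4%; one-sided 0.05.

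Normal approximation: Φ{[(0.19 − 0.094) − 1.645 × √(0.19 × 0.81/90)] / √(0.094 × 0.906/90)} = Φ{(0.096 − 0.0680)/0.0308} = Φ(0.91) = 81.8%. This reproduces the stated power of more than 80%. The exact method planned in SAP 6.2 gives 77.6% at n = 90, which is a separate matter.

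**4. The decision margin**

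The exact one-sided 95% upper limit for x events in n is the 0.95 quantile of Beta(x + 1, n − x).

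| Evaluable | Events | Upper limit | Result |
|---|---|---|---|
| 90 | 10 | 18.12% | pass |
| 90 | 11 | 19.42% | fail |
| 100 | 12 | 18.72% | pass |
| 100 | 13 | 19.87% | fail |

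One lost event changes the decision only if the full count is exactly one above the limit. At a true rate of 9.4% that has probability 8.6% (11 of 90) or 5.9% (13 of 100).

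**5. Affected subjects per 100**

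The documents give neither input. Assume that 10% to 30% of subjects have two lesions and that the study stent fails in 1% to 5% of attempts.

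- Pattern A, if every two-lesion subject has two Onyx attempts and every failure ends with another size: 100 × 0.10 × 2 × 0.01 × 0.99 = 0.2, up to 100 × 0.30 × 2 × 0.05 × 0.95 = 2.85.
- Pattern B, if every two-lesion subject has one Onyx attempt: 100 × 0.10 × 0.01 = 0.1, up to 100 × 0.30 × 0.05 = 1.5.

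**6. Events**

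Take the upper end of Pattern A and assume a 9.4% event rate at the failed lesion. A draw by attempt would bring in 2.85 × 0.094 × 0.5 = 0.13 events per 100 subjects. That is a gross figure, because the draw also passes over the successful lesion half the time. The net change is 2.85 × 0.5 × (rate at failed lesions − rate at successful lesions), which is zero if the rates are equal. It reaches 0.13 if the failed lesions' rate is 9.4 points higher.

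**7. Chance of a false pass at a true rate of 19%**

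Assume that m subjects each have a recorded TLF probability 0.10 lower than it would be with the failed lesion counted.

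| Evaluable | m = 0 | m = 1 | m = 2 | m = 3 |
|---|---|---|---|---|
| 90 | 3.2% | 3.4% | 3.6% | 3.8% |
| 100 | 4.33% | 4.55% | 4.78% | 5.03% |

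**The case against.** The strongest reply is that the plan can be read sensibly as it stands. SAP 6.1 makes ITT the default, a target lesion includes an attempted one, and the all-target-lesion analysis keeps the failed lesion visible. For Pattern B an attempt-based reading is available. This stands in part. However, the ITT default settles which subjects count and gives way where something else is specified, and SAP 6.2 specifies the lesion. The all-lesion analysis is secondary and does not decide against the 19% goal.

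Pattern A may also be rare. The switch in Protocol 5.4.6 can be read as covering only subjects with no study stent implanted. Protocol 5.4.4 requires the first lesion to be treated successfully before the second is attempted, so failures would arise mainly at the second lesion. This stands, and it makes 2.85 an upper figure.

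A reader might infer four stronger things that the documents do not support:

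- **That failed-device subjects leave the analysis, against SAP 3.1.** They stay in numerator and denominator. SAP 3.1 speaks of subjects; the mismatch concerns lesions.
- **That Pattern B drops the failed lesion by rule.** The analysis lesion is undefined, not excluded.
- **That the random algorithm would select the core-size lesion.** Its listed steps do not restrict which lesions are sorted, but the paragraph that introduces it confines the draw to subjects with two 2.0 mm lesions.
- **That the bias favours the device.** Failed delivery is not a TLF component; it is captured under device success. Lesions that resist delivery may do worse, but later events there occur with a different stent. Protocol 7.1 gives 7.9% for 2.25 mm DES and expects 9.4% for 2.0 mm, so the switched lesion could even do better. No figure in the documents settles this.

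**Conclusion.** The concern holds as a gap in the lesion-selection rule, not as a demonstrated bias. In Pattern A the literal rule selects on a post-enrolment device outcome. In Pattern B it names no lesion for a subject who must be analysed.

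The expected effect is small. On the assumed ranges, at most about 3 subjects per 100 are affected, and about 0.13 events are at issue before any offset from the other lesion. With one to three affected subjects and the assumed gap of 0.10, the false-pass chance rises by at most about 0.7 percentage points (4.33% to 5.03% with 100 evaluable; 3.2% to 3.8% with 90). It stays below 5% with 90 evaluable and about reaches 5% with 100.

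The gap still merits repair before database lock, because one event can decide a borderline result and the rule should not be settled once outcomes are known.

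**What to change.** In SAP 6.2 and Protocol 7.4, replace the two selection sentences with a rule by attempt, for example:

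> The analysis lesion is a lesion for which a Resolute Onyx 2.0 mm stent was attempted (introduced into the guide catheter for that lesion), whether or not it was implanted. If it was attempted for one lesion only, that is the analysis lesion. If it was attempted for both, the pre-specified random draw is applied to both, whichever stent was finally placed.

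In step 1 of the SAP algorithm, restrict the lesions to be sorted to those that meet this definition. State also whether an MI in the vessel of an unselected lesion counts towards primary TLF.

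No separate lesion rule is needed for the PP set, because SAP 4 already removes subjects who received no study device or who also received another type of DES.

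The cost is a short rewording in each document and a change to the lesion-selection flag. No new data are needed, since failed study stents are already recorded in the eCRF. The downside for the sponsor is that the observed rate may become slightly less favourable.

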6.3. Analysis of Secondary Endpoints

Descriptive statistics for the secondary endpoints will be provided. Categorical variables will be reported using counts and percentages, and continuous variables will be reported by giving the number of known values, the mean, standard deviation, minimum and maximum values. The time-sensitive nature of any response variable may be displayed by using a Kaplan-Meier plot. For the myocardial infarctions (MI) component of the endpoints, the extended historical MI definitions will be used.

6.4. Analysis of Baseline Characteristics

All clinically relevant baseline variables will be tabulated and reported. Categorical variables will be reported using counts and percentages, and continuous variables will be reported by giving the number of known values, the mean, standard deviation, minimum and maximum values.

6.5. Handling of Missing Data

Every effort will be undertaken to minimize missing data. In time-to-event outcomes drop-outs will be censored at the time of discontinuation, consistent with the Kaplan-Meier approach. Unless otherwise specified, no statistical techniques will be used to impute missing data for continuous or categorical characteristics and outcomes. The number of subjects included in each analysis will be reported so that the reader can assess the potential impact of missing data.

For the primary endpoint, a sensitivity analysis will be conducted to assess the impact of censored data and will include a worst-case analysis.

6.6. Analysis of Poolability and Homogeneity

Given this is a multi-center trial, to account for the pooling of results across sites the following analysis will be performed:

1. Pooling data of the small sites:

The sites with enrollment of 5 subjects or more are reported individually. The sites with enrollment of 4 or less are pooled into super-sites according to their geographical closeness so that the combined super-sites would have five or more enrolled subjects. If a super-site is with 5 or more subjects, the pooling of this supersite will stop and the pooling of the next super-site will start.

2. Assessment of baseline characteristics across sites:

Important baseline demographic and lesion characteristics (lesion-length, baseline RVD, age, sex, diabetes, history of MI and worst Canadian Cardiovascular Society Angina Class (CCSC)) will be tabulated for each site. Assessment of differences in baseline characteristics across sites

will be performed using one-way analysis of variance for continuous parameters and logistic regression for categorical parameters.

3. Analysis on the primary endpoint (TLF at 12 months) across sites:

Rates of the primary endpoint for each patient group will be presented by site and comparison across sites will be carried out using logistic regression to assess site homogeneity, with the primary endpoint as the dependent variable, and the sites as independent variable. If there is significant difference in baseline characteristics observed in step 1, then this comparison will be adjusted by adding the entire baseline variables listed above into the logistic regression model as additional independent variables.

To account for the pooling of results across regions (US vs. OUS), the following analysis will be performed:

1. Assessment of homogeneity of baseline characteristics between US and OUS cohorts:

The two-sample t-test, Fisher's exact test or CMH (Modified Ridit scores) will be used depending on the distributions of the baseline covariates. The covariates that will be considered include: lesion-length, baseline RVD, age, sex, diabetes, history of MI and worst Canadian Cardiovascular Society angina class. Statistical non-significance (significance level set at 0.15) for any of the covariates is supportive evidence of the comparability of Resolute arms without adjusting for that covariate. However, any covariate for which the group difference is deemed to be clinically and statistically significant could be adjusted by using propensity scores as discussed below to account for any covariate imbalances.

2. Assessment of Outcome Comparability:

If any of the above baseline covariates is significantly different, then the outcome of 12 months TLF rate between the two cohorts will be compared as the following: For each individual a propensity score will be calculated using logistic regression, with indicator for cohort (US, non-US) membership as the dependent variable and the above mentioned covariates as the independent variables (covariates will be included regardless of whether or not they are deemed homogenous). Patients will then be categorized into quintiles based on this propensity score. The 85% confidence interval of propensity score quintile adjusted odds ratio of region will be calculated. If the 85% confidence interval contains one (1), then the two cohorts will be considered poolable.

To account for the poolability by gender, the following analysis will be performed:

1. Assessment of homogeneity of baseline characteristics by gender:

The two-sample t-test, Fisher's exact test or CMH (Modified Ridit scores) will be used depending on the distributions of the baseline covariates. The covariates that will be considered include: lesion-length, baseline RVD, age, diabetes, history of MI and worst Canadian Cardiovascular Society angina class. Statistical non-significance (significance level set at 0.15) for any of the covariates is supportive evidence of the comparability without adjusting for that covariate. However, any covariate for which the group difference is deemed to be clinically and statistically significant could be adjusted by using propensity scores as discussed below to account for any covariate imbalances.

2. Assessment of Outcome Comparability:

If any of the above baseline covariates is significantly different, then the outcome of 12 months TLF rate between the two cohorts (male vs. female) will be compared as the following: For each individual a propensity score will be calculated using logistic regression, with indicator for cohort membership as the dependent variable and the above mentioned covariates as the independent variables (covariates will be included regardless of whether or not they are deemed homogenous). Patients will then be categorized into quintiles based on this propensity score. The

85% confidence interval of propensity score quintile adjusted odds ratio of gender will be calculated. If the 85% confidence interval contains one (1), then the two cohorts will be considered poolable.

Statistical non-significance in the primary endpoint for site, region and gender comparisons will confirm that the sites, regions and gender are homogeneous in this trial. Otherwise, the cause of the significant difference will be investigated and further analyses plan will be discussed with FDA.

7. Data Screening and Acceptance

Screening and acceptance testing of these data will be carried out in accordance with Data Management Plan. To this end, all data involved in the determination of endpoints will be screened for missing and unusual values. Any missing data that affect the ability to determine or analyze any endpoint will be queried by Data Management for confirmation of irretrievability. Unusual values, such as outliers, will also be queried, and if confirmed, will be used as recorded.

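### SAP 6.6 compares 12-month TLF by region and by gender only if a baseline covariate differs, then treats non-significance on about 8.5 expected events as confirming homogeneity

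*SAP*

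**What the plan says.** For region and for gender, SAP 6.6 works in two steps. Step 1 tests a list of baseline covariates at the 0.15 level. Step 2 is introduced by a condition. For region it reads "If any of the above baseline covariates is significantly different, then the outcome of 12 months TLF rate between the two cohorts", followed by a propensity-quintile adjusted odds ratio. For gender the condition is the same, and only under it is it said that the "12 months TLF rate between the two cohorts (male vs. female) will be compared as the following". No other branch is given in either case. The decision rule is: "If the 85% confidence interval contains one (1), then the two cohorts will be considered poolable".

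The site analysis in the same section is built differently. TLF is always tabulated ("Rates of the primary endpoint for each patient group will be presented by site") and always compared by logistic regression. Only the covariate adjustment is conditional.

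The conclusions carry no such condition. SAP 6.6 closes with "Statistical non-significance in the primary endpoint for site, region and gender comparisons will confirm that the sites, regions and gender are homogeneous". Protocol 7.4 (Analysis of the Primary Endpoint) has "Statistical non-significance in the primary endpoint for gender comparisons will confirm the homogeneity by gender in this trial", and SAP 6.2 repeats it with a pointer to the homogeneity analysis. If a difference is significant, SAP 6.6 says the cause will be investigated and further analysis discussed with FDA.

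**The concern.** The plan draws a conclusion from comparisons that it may never make. Similar baselines do not imply similar outcomes. If no covariate reaches the 0.15 level, the SAP specifies no regional interval or test of TLF, and no TLF estimate by gender. A regional rate could be added up from the site table; a gender rate could not.

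Where the comparison is made, a non-significant result on very few events shows only that the trial could not detect a difference. Followed as written, the report could state that regions or sexes are confirmed homogeneous when the odds of TLF differ twofold or more. A missed difference triggers no further step, because the investigation and the FDA discussion follow only a significant result.

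The primary hypothesis test is not at stake. What is at stake is the statement that the pooled rate applies to both regions and both sexes.

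**Working it through.** **Inputs from the documents.** SAP 3.3: 100 subjects, 10% loss to follow-up, true 12-month TLF of 9.4%. SAP 6.6: 0.15 level for baseline covariates; cohorts poolable if the 85% interval for the odds ratio (OR) contains 1. The documents give no power or event count for these comparisons, no regional or gender split, no stratified estimator and no interval method. Those are assumptions below.

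**Expected events.** 100 × 0.90 × 0.094 = 8.46.

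**How often step 2 is not reached.** If the cohorts truly do not differ and the covariates are independent (assumption), no covariate is significant in 0.85^7 = 32% of trials for region (seven covariates) and 0.85^6 = 38% for gender (six).

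**How often a real difference is called poolable.** Take two independent binomials with 90 evaluable subjects and the overall rate held at 9.4%. The interval is the unadjusted Wald one:

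log OR ± 1.440 × √(1/a + 1/b + 1/c + 1/d), with 0.5 added to all cells if any is zero.

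Exact enumeration of all outcomes gives the probability that the interval contains 1:

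| Split | Rates at OR 2, higher rate in smaller cohort | OR 2 | OR 3 | OR 2, reversed | OR 3, reversed |
|---|---|---|---|---|---|
| 45/45 | 6.5% vs 12.3% | 72.3% | 54.3% | same | same |
| 54/36 | 7.0% vs 13.0% | 71.2% | 51.3% | 77.1% | 62.7% |
| 63/27 | 7.5% vs 13.9% | 70.3% | 49.8% | 86.1% | 77.8% |
| 72/18 | 8.0% vs 14.9% | 70.9% | 51.0% | 97.3% | 97.3% |

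Reversed means that the higher rate is in the larger cohort.

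**Sensitivity to the interval method.** The 97.3% is particular to the Wald interval at 72/18. For OR 2, over all splits and both directions, profile-likelihood intervals give 65% to 70% and score intervals 65% to 81%.

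**Sensitivity to the rates.** At 7.5% versus 15% (8 to 12 expected events), the Wald figures are 64% to 68%, and 66% to 90% reversed.

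**With quintile adjustment.** This assumes a Mantel-Haenszel estimator, seven normal covariates with one shifted by 0.4 SD between cohorts, and 6,000 simulations per scenario. For OR 2 at 9.4% overall, no OR could be estimated in 3% to 6% of trials, and in 11% to 37% reversed. Among trials with an estimate, 71% to 77% were not flagged, and 83% to 96% reversed.

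**What a perfectly balanced result would show.** Take 4/45 versus 4/45. The standard error of log OR is √(2/4 + 2/41) = 0.741. The OR is 1.0 with 85% interval exp(±1.440 × 0.741) = 0.34 to 2.90. The exact 95% interval for each cohort is 2.5% to 21.2%. The difference is 0, with Newcombe 95% interval −13.0 to +13.0 percentage points. Identical observed rates would still be compatible with nearly a threefold odds ratio, and each cohort's upper limit lies above the 19% goal.

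**The case against.** The best counter-reading is that the condition governs only the propensity adjustment, not the comparison itself. SAP 6.6 says that a non-significant covariate supports comparability without adjustment, and the site analysis works that way. SAP 6.2, Protocol 7.4 and the closing sentence of SAP 6.6 all presuppose a gender comparison. This reading is possible, but it leaves the unadjusted comparison without a method, an interval or a table. The phrase about rates for each patient group in the site analysis does not fill the gap, since the term is not defined in this single-arm trial.

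It can also be said that step 2 will usually be reached. By chance alone at least one covariate would differ in 68% of trials for region and 62% for gender (1 − 0.32 and 1 − 0.38, under the same assumptions). With one of seven covariates shifted by 0.4 SD, the figure is 82% to 88%. That is fair: the unspecified case is the less common one. It is still common enough to need a rule.

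On size, the splits and estimators are assumed, the highest Wald figures are artefacts of that method, and a trial with no estimable odds ratio does not strictly meet the rule for poolability. The simulation's seven covariates match the regional model, not the six-covariate gender model. These points stand, so the conclusion should rest on the unadjusted range, not on the extremes.

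Finally, the 0.15 level is more sensitive than 0.05, the pooled test is untouched, and no trial of this size could establish homogeneity. All true. The last is the reason not to claim it.

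**Conclusion.** The concern holds. SAP 6.6 gives no method for the regional and gender TLF comparisons when baselines look alike, and its rule for reading non-significance is wrong as written. With 8.46 expected events, a true twofold difference in odds would pass as poolable in roughly two-thirds of trials or more, whichever interval method is used. With the Wald interval, a threefold difference would pass in about half of trials when the higher rate is in the smaller cohort, and more often when it is in the larger. These figures assume 90 evaluable subjects, an overall rate of 9.4% and splits between 45/45 and 72/18.

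The plan should be changed, but the primary test and its decision rule are not affected.

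There is also a clerical slip that adds no weight. The trigger for the adjusted site comparison reads "If there is significant difference in baseline characteristics observed in step 1", but step 1 there is the pooling of small sites; the baseline comparison is step 2.

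**What to change.** 1. In SAP 6.6, report 12-month TLF by region and by gender in every case, whatever the baseline p-values: the rate in each cohort with its exact 95% confidence interval, and the difference with its 95% confidence interval. Keep the propensity-quintile odds ratio as an additional analysis when baselines differ.
2. In SAP 6.2 and 6.6, replace the statement that non-significance confirms homogeneity with one that no evidence of heterogeneity was found, to be read from the width of the interval. Make the same change in Protocol 7.4 at the next amendment.
3. In the site analysis of SAP 6.6, correct the reference from step 1 to step 2.

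The cost is SAP wording and a few extra tables, with no new data. The Protocol wording can wait because, under Protocol 11.4, plan changes go to the regulatory authorities and for IRB re-approval as required. The poolability statement becomes less assertive, and the added tables describe the cohorts without adding power.
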